3.5 STUDY CALENDAR

	Screening ¹	Baseline ¹	Cycle 1 Day 1 ¹	Subsequent Cycles Day 1	28 Days Safety FU ^{10,12}	Long Term FU ^{11, 12}
Nivolumab ²				X		
VB-111 ³			Every 6 weeks			
Microsatellite stable (MSS) status ⁴	X					
Histologic confirmation of disease	X					
Medical History	X					
Height	X					
Physical exam, weight and ECOG	X		X	X	X	X
EKG	X		X	X		
HIV serology	X					
Cardiology consult ⁵	X		X	X		
Ophthalmologic exam ⁵	X					
Echocardiogram ⁵	X	X				
24-hour urine (if creatinine clearance is tested this way)	X					
TB testing ⁵	X					
Troponin I	X		X	X		
PT, INR, PTT	X		X	X	X	
Urinalysis	X					
ACTH and morning cortisol	X					
Baseline signs and symptoms		X				
HLA		X				
Concomitant medications		X	X	X		
Vital Signs	X		X ⁶	X ⁶	X	
CBC w/differential, Platelets	X		X	X	X	X
Biochemical profile ⁷	X		X	X	X	X

	Screening ¹	Baseline ¹	Cycle 1 Day 1 ¹	Subsequent Cycles Day 1	28 Days Safety FU ^{10,12}	Long Term FU ^{11, 12}
Thyroid tests TSH, T3, T4	X		X	X	X	
Uric acid, amylase and lipase	X		X	X	X	
Tumor marker CEA, AFP, CA19-9	X		X	X	X	
Serum or urine pregnancy test	X		X	X		
Radiologic Evaluation ⁸	X	X	Every 8 weeks			X
Adverse event evaluation			X	X	X	X
Tumor biopsy ⁹		X		X		
Phone call or e-mail for survival every 6 months						X

¹ Baseline and C1D1 evaluations do not need to be repeated if performed at screening or baseline in designated time frame. All evaluations will be done within 72 hours before treatment initiation on Day 1 of every cycle. If treatment does not start within 28 days after enrollment, screening evaluations will be repeated. Cycle is 14 (+/-3) days.

² 240 mg of nivolumab via IV infusion on Day 1 of each cycle starting on cycle 2.

³ 1x10¹³ VP of VB-111 IV on Day 1 of cycle 1 and every +3 cycles (4, 7, 10 and so on). Decreased dose of 0.7x10¹³ VP for patients with weight ≥ 35kg and <50 kg.

⁴ confirmed by genetic analysis or immunohistochemistry.

⁵ if clinically indicated.

⁶ For vital signs see Section 3.2.3.

⁷ Biochemical Profile: electrolytes, BUN, creatinine, AST, ALT, total and direct bilirubin, calcium, phosphorus, albumin, magnesium.

⁸ CT scan of chest, abdomen and pelvis (or MRI of chest, abdomen and pelvis if clinically indicated) on screening, baseline and every 8 (+/-1) weeks after start of study therapy. If treatment continues after initial estimation of PD, conformational scan will be done 4 weeks (+/- 1 week) later. If patient is taken off treatment for a reason other than disease progression, imaging will continue during Follow UP until disease progression.

⁹ Mandatory tumor biopsies will be performed at baseline and on Day 1 of cycle 2 or cycle 4. If the patient's disease progresses before scheduled biopsy, post-treatment biopsy may be performed per PI discretion at the time of progression

¹⁰ +/- 1 week

¹¹ Follow up visits are planned to be performed at 60 (+/- 14 days) and 90 (+/- 14 days) days after treatment discontinuation to evaluate patient's safety. After this visit, subjects will be followed every 6 months (\pm 1 month) for survival by phone call or e-mail. **NOTE:** if patient is taken off treatment for reason other than disease progression, we will continue to invite patient every 8 (+/-1) weeks for imaging studies. Outside scans are acceptable.

¹² If subjects are not willing to come to NIH for FU visits, they will be contacted by phone call or e-mail for survival and adverse events.

3.6 COST AND COMPENSATION

3.6.1 Costs

NIH does not bill health insurance companies or participants for any research or related clinical care that participants receive at the NIH Clinical Center. If some tests and procedures performed outside the NIH Clinical Center, participants may have to pay for these costs if they are not covered by insurance company. Medicines that are not part of the study treatment will not be provided or paid for by the NIH Clinical Center.

3.6.2 Compensation

N/A

3.6.3 Reimbursement

This study offers subject reimbursement or payment for travel, lodging and/or meals while participating in the research. The amount, if any, is guided by NIH policies and guidelines.

On this study, the NCI will cover the cost for some of the expenses. Some of the costs may be paid directly by the NIH and some may be reimbursed to the subject. Someone will work with subjects to provide more information.

3.7 CRITERIA FOR REMOVAL FROM PROTOCOL THERAPY AND OFF STUDY CRITERIA

Prior to removal from study, efforts must be made to have all subjects complete a safety visit approximately 90 days following the last dose of study therapy.

3.7.1 Criteria for Removal from Protocol Therapy:

- Participant requests to be withdrawn from active therapy
- Unacceptable toxicity as described in Section [3.3](#)
- Positive pregnancy test or intent to become pregnant
- Investigator discretion
- Initiation of therapy that prevents further administration of study treatment
- Progressive Disease. NOTE: While RECIST PD will be noted and recorded, the immune-related RECIST criteria ([Appendix B](#)) and conformational scan will be applied to determine discontinuation of study treatment.
- Intercurrent illness that prevents further administration of treatment.

3.7.2 Off Study Criteria

- Lost to follow-up
- Death
- Participant requests to be withdrawn from study
- Investigator discretion
- PI decision to end the study

3.7.3 Lost to Follow-up

A participant will be considered lost to follow-up if he or she fails to return for 3 scheduled visits and is unable to be contacted by the study site staff.

The following actions must be taken if a participant fails to return to the clinic for a required study visit:

- The site will attempt to contact the participant and reschedule the missed visits and counsel the participant on the importance of maintaining the assigned visit schedule and ascertain if the participant wishes to and/or should continue in the study.
- Before a participant is deemed lost to follow-up, the investigator or designee will make every effort to regain contact with the participant (telephone calls and if necessary, a certified letter to the participant's last known mailing address or local equivalent methods). These contact attempts should be documented in the participant's medical record or study file.

Should the participant continue to be unreachable, he or she will be considered to have withdrawn from the study with a primary reason of lost to follow-up.

4 CONCOMITANT MEDICATIONS/MEASURES

All routine and appropriate supportive care (including blood products) will be provided during this study, as clinically indicated, and in accordance with the standard of care practices. Clinical judgment should be utilized in the treatment of any AE experienced by the patient.

4.1 EXCLUDED CONCOMITANT MEDICATIONS

Prohibited medication/class of drug	Usage
Any investigational anticancer therapy other than those under investigation in this study	Should not be given concomitantly whilst the patient is on study treatment
mAbs against CTLA-4, PD-1, or PD-L1 other than those under investigation in this study	Should not be given concomitantly whilst the patient is on study treatment
Any concurrent chemotherapy, radiotherapy, immunotherapy, or biologic or hormonal therapy for cancer treatment other than those under investigation in this study	Should not be given concomitantly whilst the patient is on study treatment. (Concurrent use of hormones for non- cancer-related conditions [e.g. insulin for diabetes and hormone replacement therapy] is acceptable. Local treatment of isolated lesions, excluding target lesions, for palliative intent is

	acceptable [e.g. by local surgery or radiotherapy])
Immunosuppressive medications including, but not limited to, systemic corticosteroids at doses exceeding 10 mg/day of prednisone or equivalent, methotrexate, azathioprine, and tumor necrosis factor- α blockers	Should not be given concomitantly. (Use of immunosuppressive medications for the management of IP-related AEs, premedication for patients who had infusion reaction, or in patients with contrast allergies is acceptable). In addition, use of inhaled, topical, and intranasal corticosteroids is permitted.

4.2 METHODS OF CONTRACEPTION

4.2.1 Female patient of child-bearing potential

Females of childbearing potential who are sexually active with a non-sterilized male partner must use effective method of contraception (**Table 6**) from the time of screening and must agree to continue using such precautions for 5 months after the last dose of nivolumab + VB-111 combination therapy. Non-sterilized male partners of a female patient must use male condom plus spermicide throughout this period. Cessation of birth control after this point should be discussed with a responsible physician. Not engaging in sexual activity for the total duration of the drug treatment and the drug washout period is an acceptable practice; however, periodic abstinence, the rhythm method, and the withdrawal method are not acceptable methods of birth control. Female patients should also refrain from breastfeeding throughout this period.

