Creatinine OR Measured or calculated creatinine clearance (CrCl) (eGFR may also be used in place of CrCl) ^Δ	$< 1.5 \times$ institution upper limit of normal OR $\geq 50 \text{ mL/min/1.73 m}^2$ for participant with creatinine levels $\geq 1.5 \times$ institutional ULN
^Δ Creatinine clearance (CrCl) or eGFR should be calculated per institutional standard.	

- The effects of nivolumab and VB-111 on the developing human fetus are unknown. For this reason, women of child-bearing potential and men must agree to use adequate contraception as defined in section 4.2 prior to study entry and for the duration of study participation and up to 5 months (women) and 7 months (men) after the last dose of the nivolumab or 2 months after the last dose of VB-111 whichever is the longer time period. Should a woman become pregnant or suspect she is pregnant while she or her partner is participating in this study, she should inform her treating physician immediately.
- Troponin level in normal range at the time of enrollment.
- Patient must be able to understand and willing to sign a written informed consent document.
- Weight $> 35\text{kg}$
- Patients must be enrolled in tissue collection protocol 11C0112.

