3 STUDY IMPLEMENTATION

3.1 STUDY DESIGN

The proposed study is an open label, single-arm phase II study of VB-111 in combination with anti-PD1, nivolumab, in patients with advanced, refractory CRC.

Treatment will be delivered in cycles consisting of 2 weeks (+/- 3 days).

VB-111 will be administered every 6 weeks starting on cycle 1 day 1 and nivolumab will be administered every 2 weeks starting on cycle 2 day 1 ([Schema 1](#) and [Table 5](#)).

[figure not shown]
Treatment will continue until off treatment criteria are met (see Section [3.7.1](#))

If one of the study drugs is permanently discontinued because of toxicity, the patient may continue the other study drug per PI discretion until off treatment criteria are met (Section [3.7.1](#)).

Patients will be monitored every 8 (+/- 1) weeks with imaging.

Treatment will be delivered without planned hospitalization. Admission for logistical reasons is allowed (i.e. if patients cannot travel home the same day or biopsies are scheduled etc.)

Patients will have two mandatory research biopsies: at baseline and either day 1 of cycle 2 (post VB-111 but pre-checkpoint inhibitor treatment) or day 1 of cycle 4 (post-VB-111 and checkpoint inhibitor treatments). Timing of the research biopsy will be determined in an alternating fashion by the research team on a 1:1 basis; i.e. the team will assign patient #1 to early second biopsy (day 1 of cycle 2), patient #2 to late second biopsy (day 1 of cycle 4) and so on.

Schema 1: Study design. Patients will undergo pre-treatment biopsy and one post-treatment biopsy at Day 1 of Cycle 2 or Day 1 of Cycle 4.

Table 5: Treatment regimen

VB-111, every 6 weeks	Nivolumab, every 2 weeks
1x10 ¹³ VP IV (for patients with weight ≥ 50kg)	240 mg IV
0.7x10 ¹³ VP IV (for patients with weight > 35kg and <50 kg)	

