4.2.2 Male patient with a female partner of child-bearing potential

Non-sterilized males who are sexually active with a female partner of childbearing potential must use a male condom plus spermicide from screening through 7 months after the last dose of nivolumab + VB-111 combination therapy. Not engaging in sexual activity is an acceptable practice; however, occasional abstinence, the rhythm method, and the withdrawal method are not acceptable methods of contraception. Male patients should refrain from sperm donation throughout this period.

Female partners (of childbearing potential) of male patients must also use a highly effective method of contraception throughout this period (**Table 6**).

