8.6.2 Paternal exposure

Male patients should refrain from fathering a child or donating sperm during the study and for 7 months after the last dose of nivolumab or 2 months after the last dose of VB-111 whichever is the longer time period.

Pregnancy of the patient's partner is not considered to be an AE. However, the outcome of all pregnancies (spontaneous miscarriage, elective termination, ectopic pregnancy, normal birth, or congenital abnormality) occurring from the date of the first dose until 7 months after the last dose of nivolumab or 2 months after the last dose of VB-111 should, if possible, be followed up and documented.

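### Sections 4.2.1 and 4.2.2 count the contraception period from the last combination dose, but sections 2.1.1 and 8.6.2 count it per drug, so the end dates can differ when one drug is continued alone

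*Combined protocol and SAP*

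**What the plan says.** For women, protocol section 4.2.1 sets the end of precautions by a single clock: "using such precautions for 5 months after the last dose of nivolumab + VB-111 combination therapy". The breastfeeding limit is tied to the same period. For men, section 4.2.2 runs "from screening through 7 months after the last dose of nivolumab + VB-111 combination therapy", and the limit on sperm donation is tied to that period.

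Section 2.1.1 sets the period differently. Precautions apply "prior to study entry and for the duration of study participation" and then for "5 months (women) and 7 months (men) after the last dose of the nivolumab or 2 months after the last dose of VB-111", with the longer of the two governing. The same sentence refers to section 4.2 for what counts as adequate contraception.

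Section 8.6.2 covers male patients only. It restricts fathering a child and sperm donation until "7 months after the last dose of nivolumab or 2 months after the last dose of VB-111 whichever is the longer time period". Its window for following up partner pregnancies uses the same two clocks.

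Section 4.3, on blood donation, uses a third wording: 5 months (women) or 7 months (men) from the last dose of nivolumab or VB-111, with no separate VB-111 interval.

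Section 3.1 says that if one drug is permanently stopped for toxicity, "the patient may continue the other study drug per PI discretion until off treatment criteria are met". Section 3.3 allows the same and argues in its favour. No maximum treatment duration is stated.

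**The concern.** While both drugs are given and stopped together, the two anchors point to about the same date. They separate once a patient continues on one drug, because the last dose of the combination then comes before the last dose of study treatment. Single-drug continuation is a planned pathway: section 3.3.1 lists many reasons to stop nivolumab permanently, and section 3.3.2 does the same for VB-111.

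Section 2.1.1 calls the fetal effects of both drugs unknown, so the end date matters to the patient. Staff who open the dedicated contraception section could give a different date from staff who open the eligibility criteria. For men, one restriction, sperm donation, is stated in sections 4.2.2 and 8.6.2 with two different anchors.

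Section 4.2 may also have no anchor at all. Nivolumab starts at cycle 2, and section 10.3 provides for patients who receive only one of the agents. A patient who leaves after the first VB-111 dose has had no combination dose to count from.

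**Working it through.** The plan states no figure to reproduce. The check compares end dates under each wording.

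**Inputs.** Post-treatment intervals: 5 months (women) and 7 months (men) in sections 4.2.1, 4.2.2 and 2.1.1; 2 months for VB-111 in section 2.1.1. Schedules: nivolumab every 14 days (section 3.2.2) and VB-111 every 42 days (section 3.2.1).

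**Convention.** Month 0 is the last dose given as the combination, *t* is the number of months one drug is then given alone, and *m* is 5 (women) or 7 (men). One month is 365.25/12 = 30.44 days.

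**Formulas.**
- Section 4.2, read literally: end = *m*, whatever *t* is.
- Section 2.1.1, nivolumab alone: end = *t* + *m*.
- Section 2.1.1, VB-111 alone: end = max(*m*, *t* + 2).

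**End of precautions, in months after the last combination dose.**

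| *t* | Women: 4.2 | Women: 2.1.1, nivolumab alone | Women: 2.1.1, VB-111 alone | Men: 4.2 | Men: 2.1.1, nivolumab alone | Men: 2.1.1, VB-111 alone |
|---|---|---|---|---|---|---|
| 3 | 5 | 8 | 5 | 7 | 10 | 7 |
| 6 | 5 | 11 | 8 | 7 | 13 | 8 |
| 9 | 5 | 14 | 11 | 7 | 16 | 11 |
| 12 | 5 | 17 | 14 | 7 | 19 | 14 |

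**When the sections differ.**
- Nivolumab alone: (*t* + *m*) − *m* = *t*. Section 4.2 ends earlier by the whole length of single-drug treatment, however short.
- VB-111 alone: section 4.2 ends earlier only if *t* + 2 > *m*, that is *t* > 3 months (women) or *t* > 5 months (men). Below that the dates coincide.

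**When section 4.2, taken alone, ends before the last dose.** This needs *t* > *m*.
- Women: 5 × 30.44 = 152 days. The first dose after that is the 11th nivolumab dose (11 × 14 = day 154) or the 4th VB-111 dose (4 × 42 = day 168).
- Men: 7 × 30.44 = 213 days. The first dose after that is the 16th nivolumab dose (16 × 14 = day 224) or the 6th VB-111 dose (6 × 42 = day 252).

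**If combination therapy loosely means any study treatment.** Section 4.2 then ends at *t* + *m*. That matches section 2.1.1 for nivolumab alone but not for VB-111 alone. For a woman with *t* = 6 it gives 6 + 5 = 11 months against 8. For a man with *t* = 9 it gives 9 + 7 = 16 months against 11. Under this reading section 4.2 ends later, so neither reading brings the sections into agreement.

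**The case against.** A reader might infer that the protocol lets contraception lapse while a patient is still being dosed. The documents as a whole do not support that, for four reasons.

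- Section 2.1.1 requires precautions "prior to study entry and for the duration of study participation", and a patient continuing one drug is still participating. A patient held to that section has no on-treatment gap. Its reference to section 4.2 most naturally imports the methods, since that section is headed as methods of contraception and section 2.1.1 states its own duration.
- In describing abstinence, section 4.2.1 speaks of the whole of drug treatment plus a washout, which suggests the authors had all dosing in mind. It also says that stopping birth control should be discussed with a physician.
- The study calendar marks a pregnancy test on day 1 of each cycle, and section 3.7.1 makes a positive test a reason to stop therapy. These limit the on-treatment risk in women but do not replace contraception, and the calendar marks no test at the follow-up visits.
- The accrual ceiling is 27 patients with refractory disease. Those affected must continue on one drug and also be women of child-bearing potential or men with such partners.

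Two further limits apply. Section 8.6.2 says nothing about women, so for them the conflict is between sections 4.2.1 and 2.1.1 alone. A partner-pregnancy follow-up window longer than the precaution window is cautious and not a fault in itself.

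All of this stands, and it removes the claim of an on-treatment lapse. It does not make the stated end dates agree.

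**Conclusion.** The inconsistency is real and bears mainly on the period after treatment. With nivolumab continued alone, section 4.2 read literally ends earlier than section 2.1.1 by exactly the length of single-drug treatment. With VB-111 continued alone, it ends earlier only beyond 3 months (women) or 5 months (men). An end date before the last dose needs section 4.2 read in isolation and more than 5 months (women) or 7 months (men) on one drug.

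These results rest on the literal wording of section 4.2 and on both drugs' last joint dose falling on one day. The documents give no expected frequency of single-drug continuation. That few patients will be affected is a judgement from the accrual ceiling and the population. Sample size, error rates and the efficacy and safety analyses are untouched. The point is still worth correcting, because two stated rules on fetal exposure disagree.

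**What to change.** Reconcile sections 2.1.1, 4.2.1, 4.2.2, 4.3 and 8.6.2 so that each restriction (contraception, breastfeeding, sperm donation, fathering a child, partner-pregnancy follow-up, blood donation) has one consistent anchor dose. The wording should state what applies to a patient who continues on one drug after the other is stopped, and to one who only ever receives one drug. Which duration and which anchor to adopt is for the sponsor and investigators to decide, and none is proposed here.

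The cost is about one sentence in each section, submitted as a protocol amendment. The consent pages were not available for this review. If they state the period, they should be checked against the reconciled text.

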4.2.2 Male patient with a female partner of child-bearing potential

Non-sterilized males who are sexually active with a female partner of childbearing potential must use a male condom plus spermicide from screening through 7 months after the last dose of nivolumab + VB-111 combination therapy. Not engaging in sexual activity is an acceptable practice; however, occasional abstinence, the rhythm method, and the withdrawal method are not acceptable methods of contraception. Male patients should refrain from sperm donation throughout this period.

Female partners (of childbearing potential) of male patients must also use a highly effective method of contraception throughout this period (**Table 6**).

4.2.3 Highly effective methods of contraception

Highly effective methods of contraception, defined as one that results in a low failure rate (i.e. less than 1% per year) when used consistently and correctly are described in **Table 6**. Note that some contraception methods are not considered highly effective (e.g. male or female condom with or without spermicide; female cap, diaphragm, or sponge with or without spermicide; non-copper containing intrauterine device; progestogen-only oral hormonal contraceptive pills where inhibition of ovulation is not the primary mode of action [excluding Cerazette/desogestrel which is considered highly effective]; and triphasic combined oral contraceptive pills).

Table 6: Highly effective methods of contraception (<1% failure rate)

Barrier/Intrauterine methods	Hormonal Methods

 • Copper T intrauterine device • Levonorgestrel-releasing intrauterine system (e.g. Mirena®)^a 	
 • Etonogestrel implants: e.g. Implanon or Norplant • Intravaginal device: e.g. ethinylestradiol and etonogestrel • Medroxyprogesterone injection: e.g. Depo-Provera • Normal and low dose combined oral contraceptive pill • Norelgestromin/ethinylestradiol transdermal system • Cerazette (desogestrel)

^a This is also considered a hormonal method

4.3 BLOOD DONATION

Subjects should not donate blood while participating in this study, and for 5 months (women) and 7 months (men) after the last dose of nivolumab or VB-111 therapy.

